4.4.2 Long-Term Follow-Up

Once subjects progress or start use of alternative anticancer therapy—for all subjects who have not withdrawn consent—they will be contacted approximately every 3 months (12 weeks) from the date of last dose by clinic visit or telephone, to assess survival and the use of alternative anticancer therapy until death or lost to follow-up.

4.5 MISSED EVALUATIONS

Missed evaluations should be rescheduled and performed as close to the original scheduled date as possible. An exception is made when rescheduling becomes, in the investigator's opinion, medically unnecessary or unsafe because it is too close in time to the next scheduled evaluation. In that case, the missed evaluation should be abandoned.

5.0 STATISTICAL METHODS OF ANALYSIS

5.1 GENERAL CONSIDERATIONS

Descriptive statistics will be used to summarize baseline demographic and disease characteristics, study drug administration, efficacy, and safety outcomes, PK parameters, and PD markers. Descriptive summaries of discrete data will present the sample size and the incidence as a frequency and as a percentage. Descriptive summaries of continuous data will present the sample size, group mean, standard deviation, median, and range. CIs will be included as appropriate. There are 2 timepoints for analyses: (1) the interim analysis will occur approximately 8 weeks (2 cycles) after the 12th subject has been enrolled in each cohort in the Phase 1b portion of the study, and (2) the final analysis will occur 24 weeks after the last subject is enrolled to the study.

Note: Under Amendment 2 of the protocol, the 2nd interim analysis will be performed approximately when 7 additional non-EIAED subjects complete 16 weeks (4 cycles) of treatment.

Statistical Basis for the Sample Size

The sample size for this study included subjects enrolled in Phase 1b and Phase 2 treated with the same dose regimen. An ORR observed in standard of care for second-line therapies (CCNU) ranged around 5 to 10%. While bevacizumab (Avastin) demonstrated an ORR >20%, considerable toxicities were reported. To reject the null hypothesis of ORR ≤5% in favor of an alternative hypothesis that the ORR is ≥20%, 43 subjects will preserve approximately 88% power to detect the difference at a 0.025 significance level by a 1-sided exact test.

Note: Under Amendment 2 of the protocol, the sample size for this study will include subjects enrolled in Phase 1b and Phase 2 and treated with the same dose regimen. Subjects enrolled in Phase 1b but treated with a different dose regimen not chosen for investigation in Phase 2, will not be included in these sample size calculations.

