Treatment can continue until the end of trial, defined as 52 weeks after the last subject is enrolled to the study, for subjects without disease progression and who are tolerating therapy. Subjects who have **confirmed** progressive disease or who start new anticancer therapy for GBM will discontinue study treatment.

[figure not shown]
Subjects who are *still on treatment at the end of the study* and deriving clinical benefit from acalabrutinib treatment may continue treatment. *At the time of the final data cutoff (DCO) and database closure, subjects who remain in this study may be transitioned to a separate rollover study or remain within this study for continued access to study drug. Once all active subjects are eligible to continue to receive acalabrutinib and after database closure, this study would be considered closed. There will be no further data collection other than reporting of SAEs per [Section 6.2](#). Access within this study will enable continued treatment with visit assessments per standard of care, whereas the separate rollover study will enable treatment continuation with visit assessments and data collection per the rollover study protocol.*

Refer to [Appendix 1](#) for a comprehensive list of study assessments and their timing. The study schema is provided below ([Figure 3-1](#)).

Note: Under Amendment 2 of the protocol, an interim analysis was scheduled after the 12th subject was enrolled in each arm (n=24). However, due to the paucity of EIAED-treated subjects, an interim analysis was held after 16 non-EIAED subjects and 1 subject on EIAED were enrolled in the study. The first interim analysis did not raise any safety concerns and showed some response in the 200 mg-BID group, while no response in 400-mg QD group. Therefore, the SAC recommended discontinuing Cohort 2 (400 mg QD) and enrolling 7 additional non-EIAED subjects planned for Phase 1b of the study into Cohort 1 (200 mg BID). A second interim analysis for safety and efficacy will be performed after enrolling an additional 7 subjects, once 15 total subjects enrolled in the 200-mg BID cohort (8 subjects enrolled prior to first interim analysis, and an additional 7 subjects planned to complete Phase 1b). An ORR rate of 3/15 (20%) will yield a lower bound of a 1-sided 90% exact binomial CI of 7.1%, which is greater than 5% (ORR estimate for the standard of care CCNU). Based on these

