criteria, the SAC and the Safety Review Committee will review data after the 2nd interim analysis and will make a recommendation if study should be continued into Phase 2. If continued, up to 28 additional subjects may be enrolled for a total of 43 subjects on the 200-mg BID dose (15 subjects from Phase 1b and 28 subjects from Phase 2) in order to complete Phase 2. The final analysis will occur 24 weeks after the last subject is enrolled in the study. Treatment will continue until the last enrolled subject experiences disease progression.

Figure 3-1. Study Schema

*Note: Per Protocol Amendment #2, the Scientific Advisory Committee (SAC) observed that response and disease-control rate observed in the 200 mg BID cohort were numerically higher than in the 400 mg QD cohort. Therefore, the 400 mg QD cohort is discontinued.

**Note: Per Protocol Amendment #2, enzyme-inducing antiepileptic drugs (EIAEDs) are no longer considered the standard of care for patients with glioblastoma (Ref. NCCN guidelines version 1 2016). As a result, the requirement for subjects (4 subjects in the 200 mg BID cohort and 3 subjects in the 400 mg QD cohort to receive EIAEDs has been eliminated. One subject receiving EIAEDs has already been enrolled into the 400 mg QD cohort) and will continue to receive treatment per protocol.

BID = twice per day; CYP = cytochrome P450; EIAEDs = enzyme-inducing antiepileptic drugs; GBM = glioblastoma multiforme; ORR = overall response rate; QD = once per day.

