## **3 STUDY OVERVIEW**

### **3.1 Study Design**

This Phase 1b/2, multicenter, open-label study was designed to evaluate the efficacy and safety of acalabrutinib in subjects with recurrent GBM who had progressed after 1 or

2 prior systemic treatment regimens. Subjects meeting the eligibility criteria for the study were assigned 1:1 to one of the following cohorts:

Cohort 1: acalabrutinib 200 mg administered PO BID

Cohort 2: acalabrutinib 400 mg administered PO QD

Under original protocol, an interim analysis was scheduled after the 12th subject was enrolled in each arm (n=24). If acceptable safety and efficacy (e.g., 2 or more of the 12 subjects [ $\geq 16.7\%$ ] achieve a complete response [CR] or partial response [PR]; additional criteria may be considered by the SAC) are observed in either cohort, the sponsor may choose to expand the study to a total of 72 subjects. The acalabrutinib dosage for the Phase 2 portion of the study will be based on available safety and efficacy data from the Phase 1b cohorts. However, due to the paucity of EIAED-treated subjects, an interim analysis was held after 16 non-EIAED subjects and 1 subject on EIAED were enrolled in the study. The first interim analysis did not raise any safety concerns and showed some response in the 200 mg BID group, while no response in 400 mg QD group. Therefore, the SAC recommended discontinuing Cohort 2 (400 mg QD) and enrolling 7 additional non-EIAED subjects planned for Phase 1b of the study into Cohort 1 (200 mg BID). Under amendment 2 of the protocol, a second interim analysis for safety and efficacy was performed after enrolling an additional 7 subjects, once 15 total subjects enrolled in the 200 mg BID cohort (8 subjects enrolled prior to first interim analysis, and an additional 7 subjects planned to complete Phase 1b).

Under amendment 2 of the protocol, the efficacy criteria for success for phase 1b was as follows: an ORR rate of 3/15 (20%) with a lower bound of a 1-sided 90% exact binomial confidence interval of 7.1% would warrant a recommendation to expand study to phase 2 an enroll additional 28 subjects. Using these criteria, a lower bound of confidence interval of 7.1% would be greater than 5% (ORR estimate for the standard of care CCNU). Based on these criteria, the SAC and the Safety Review Committee did not recommend continuing the study (initiating Phase 2) after reviewing the results of the 2nd interim analysis.

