### **3.2 Sample Size**

The sample size for the overall study included subjects enrolled in Phase 1b and Phase 2 treated with the same dose regimen. An ORR observed in standard of care for second-line therapies (CCNU) ranged around 5 to 10%. While bevacizumab (Avastin)

demonstrated an ORR > 20%, considerable toxicities were reported. To reject the null hypothesis of ORR ≤ 5% in favor of an alternative hypothesis that the ORR is ≥ 20%, 43 subjects will preserve approximately 88% power to detect the difference at a 0.025 significance level by a 1-sided exact test.

However, the initiation of part 2 of the study was dependent on the results of part 1b. The sample size for part 1b was chosen empirically to be 24 subjects. Furthermore, the sample size for subjects treated with acalabrutinib dose of 200mg BID was 15, while 9 subjects were treated with acalabrutinib dose of 400 mg. The sample size and design changes for part 1b are summarized in the table below:

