## **4.3 Exploratory Endpoints**

## **5 HYPOTHESES AND MULTIPLICITY**

No hypothesis will be tested and no multiplicity adjustments will be made.

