### **10.7.1 Best Overall Response, Disease Control Rate and Overall Response Rate per RANO criteria**

Measurable disease (bidimensional) as defined by the RANO criteria. RANO criteria (Wen 2010) will be followed for selection of measurable and non-measurable lesions and about the number of lesions to be assessed, as well as for the assessments of response and progression.

Disease Control Rate (DCR) is defined as the proportion of subjects who achieve a best response of SD, PR or CR at any point of the study.

Overall response Rate (ORR) is defined as the proportion of subjects who achieve a best response of PR or CR at any point of the study.

The primary analysis of DCR and ORR will be conducted using safety analysis set. DCR and ORR will be calculated with the corresponding exact binomial 2-sided 95% CI and 1-sided 90% CI (or 2-sided 80% CI) for treatment cohort.

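### The 88% power is a single-stage figure for 43 subjects; if the Phase 1b criterion of 3/15 is followed, power at ORR 20% is about 58% and the chance of a no-go about 40%, and neither document says so

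*Protocol*

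**What the plan says.** Protocol 5.1 tests a null ORR of at most 5% against an alternative of at least 20% and states that "43 subjects will preserve approximately 88% power to detect the difference at a 0.025 significance level by a 1-sided exact test". The synopsis repeats this, and SAP 3.2 carries the same claim ("43 subjects will preserve approximately 88% power").

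The Amendment 2 note in Protocol 3.0 builds the 43 from 15 Phase 1b subjects on 200 mg BID and up to 28 Phase 2 subjects. A second interim analysis falls between the two groups. Its efficacy criterion reads "An ORR rate of 3/15 (20%) will yield a lower bound of a 1-sided 90% exact binomial CI of 7.1%, which is greater than 5" per cent, the 5% being the reference ORR for lomustine. On that basis the two committees "will make a recommendation if study should be continued into Phase 2".

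SAP 3.1 treats 3/15 as the Phase 1b success criterion and reports the outcome: "Based on these criteria, the SAC and the Safety Review Committee did not recommend continuing the study (initiating Phase 2" being the step not taken). SAP 3.2 acknowledges that "the initiation of part 2 of the study was dependent on the results of part 1b" and says that the Phase 1b size was chosen empirically. It leaves the 88% as it stands. Neither document gives a go or no-go probability, a power that allows for the interim, or a statement that the 88% ignores it.

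**The concern.** A power figure should describe the design that will be run. Here the first 15 of the 43 subjects also decide whether the other 28 are enrolled. A trial stopped at 15 cannot reject the null at 43, so the chance of passing the Phase 1b criterion caps the power.

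What is at stake is how the stop is read. Phase 2 was not started, so the Phase 1b decision is the trial's working efficacy conclusion. Beside an unqualified 88%, a reader may suppose that a drug with ORR 20% would give this result only about 12% of the time (1 − 0.88). Whether that is so depends on the operating characteristics of 3/15, which are not stated.

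**Working it through.** **Inputs.** Null ORR 0.05, alternative 0.20, n = 43, one-sided exact alpha 0.025 (Protocol 5.1). Stage sizes 15 and 28, criterion 3/15, reference rate 5% (Protocol 3.0). All treated subjects are in the denominator (Protocol 5.2). The final cut-off is not printed and is derived in step 1.

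**1. Reproduce the plan's figure.** Let X be Binomial(43, p).
- P(X ≥ 5 | 0.05) = 0.0623, which exceeds 0.025.
- P(X ≥ 6 | 0.05) = 0.0194, so the cut-off is 6.
- P(X ≥ 6 | 0.20) = 0.885.

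The stated 88% is the single-stage power.

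**2. Smallest count that meets the Phase 1b criterion.** The exact (Clopper-Pearson) one-sided 90% lower limit for r/15 is the 0.10 quantile of Beta(r, 16 − r).
- r = 2: 3.6%, below 5%.
- r = 3: 7.6%, above 5%. The protocol prints 7.1%; both values clear 5%, so the criterion is unchanged.

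The minimum is 3.

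**3. Go and no-go at ORR 20%.** With X1 Binomial(15, 0.20), P(X1 ≥ 3) = 0.602 and P(X1 ≤ 2) = 0.398.

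**4. Power if the criterion is followed.** Sum over x1 from 3 to 15 of P(X1 = x1) × P(X2 ≥ 6 − x1), with X2 Binomial(28, 0.20):

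| x1 | P(X1 = x1) | P(X2 ≥ 6 − x1) | Product |
|---|---|---|---|
| 3 | 0.25014 | 0.93883 | 0.23484 |
| 4 | 0.18760 | 0.98453 | 0.18470 |
| 5 | 0.10318 | 0.99807 | 0.10298 |
| ≥ 6 | 0.06105 | 1 | 0.06105 |
| Total | | | **0.58357** |

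A simulation of 2,000,000 trials gave 0.583. The power lost is 0.88545 − 0.58357 = 0.30188: trials with 0 to 2 responses in the first 15 that would have reached 6 of 43 had they continued. By the same sum at ORR 5%, type I error falls from 0.0194 to 0.0075.

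**5. Criterion overruled.** If a fraction q of no-go results is overruled, independently of the count, power = 0.58357 + q × 0.30188.
- q = 0.25: 0.659
- q = 0.50: 0.735
- q = 0.75: 0.810
- q = 1: 0.885

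The documents give no value for q.

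**6. Allowing for responses already seen.** The 15 include the eight Cohort 1 subjects reviewed at the first interim analysis, which showed some response in that cohort. The count is not given, so these are scenarios at ORR 20%, with 7 and then 28 further subjects:

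| Responses in first 8 | No-go | Power |
|---|---|---|
| at least 1 | 0.307 | 0.673 |
| exactly 1 | 0.577 | 0.405 |
| exactly 2 | 0.210 | 0.763 |

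With three or more, the criterion would already have been met.

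**7. What a no-go count says about 20%.** Exact two-sided upper limits for n = 15:

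| Responses | 95% upper limit | 80% upper limit |
|---|---|---|
| 0 | 21.8% | 14.2% |
| 1 | 31.9% | 23.6% |
| 2 | 40.5% | 31.7% |

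No count below 3 excludes 20% at the 95% level. Only 0/15 does so at the 80% level.

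**The case against.** The other side has four arguments.

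- **The 88% is not miscalculated.** It is attached to 43 subjects, and SAP 3.2 says openly that the second part depended on the first. This stands: the defect is a missing operating characteristic, not a wrong sum. But the 88% and the dependency sit in consecutive paragraphs and are never connected, and the reader cannot tell how far power falls.
- **The criterion is advisory, and the committees weigh safety as well.** This stands too, and it is why the result is a range. The top of the range needs every no-go to be overruled, whereas SAP 3.1 reports a decision that followed the criteria.
- **The 58% and 40% treat the 15 as a fresh sample, when some response had been seen by the time 3/15 was adopted.** This is the strongest point. The unconditional pair is neither an upper nor a lower bound and must carry that caveat. It does not rescue the 88%: with one or two early responders the no-go probability is 0.577 or 0.210, both well above 12%.
- **Little depends on it now.** The SAP says "No hypothesis will be tested and no multiplicity adjustments will be made", the 43-subject test will not be run, and the planned intervals would themselves show that 1 or 2 of 15 does not exclude 20%. That limits the consequence to interpretation. The stated power remains unqualified in three places.

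**Conclusion.** The concern holds and should be fixed. The 88% is right for a single-stage test of 43 subjects but describes the staged design only if every no-go is overruled. With the 3/15 criterion followed, power at ORR 20% is 0.584 and the no-go probability is 0.398, so the stop is roughly a four-in-ten event for a drug at the design alternative, not a one-in-eight event. Being advisory, the criterion puts power anywhere from about 58% to 88%.

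These figures assume independent binomial responses, a final cut-off of 6/43 and a fresh sample of 15. They ignore the choice between cohorts and the responses in the first eight. No planned analysis is invalidated; the point concerns the stated power and the reading of the no-go.

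**What to change.** Add text to SAP 3.2 and the CSR along these lines:

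> The 88% is the power of a single-stage test of 43 subjects (reject at 6 or more responses; attained one-sided alpha 0.0194). If the Phase 1b criterion of at least 3/15 is followed, overall power at ORR 20% is about 58% and the probability of a no-go at ORR 20% is about 40%. The criterion is advisory. These figures treat the 15 subjects as a fresh sample, although some response had been seen in the first eight.

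Keep 0.0194 as the type I error and take no credit for non-binding futility stopping. In the CSR, state that the no-go alone does not exclude an ORR of 20%, and show the observed count with the exact two-sided 95% interval. SAP 10.7.1 already plans that interval: "DCR and ORR will be calculated with the corresponding exact binomial 2-sided 95% CI and 1-sided 90% CI (or 2-sided 80% CI" being the companion).

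The cost is a few sentences, with no patients, data or new analysis. Changing the synopsis and Protocol 5.1 would need an amendment submitted to the IRB/IEC (Protocol 7.8), so those edits should wait for any later amendment.

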5.2 DEFINITION OF ANALYSIS SETS

All efficacy and safety analysis will be performed using the safety population, which consists of all subjects who receive any amount of study treatment. The analysis of DOR will only include subjects who have achieved objective response.

5.3 MISSING DATA HANDLING

No imputation of values for missing data will be performed except that missing or partial start and end dates for AEs and concomitant medication will be imputed according to prespecified, conservative imputation rules. Subjects lost to follow-up (or drop out) will be included in statistical analyses to the point of their last evaluation.

5.4 ENDPOINT DATA ANALYSIS

5.4.1 Safety Endpoint

Verbatim descriptions of AEs will be mapped according to the MedDRA thesaurus terms and graded according to the National Cancer Institute (NCI) CTCAE, v4.03 or higher. Extent of exposure to study drug, all AEs, SAEs, non-SAEs leading to study drug discontinuation, and study drug-related AEs will be summarized. The frequency of AEs will be summarized by system organ class and preferred terms according to MedDRA,

as well as per severity per NCI CTCAE grade. Only treatment-emergent AEs will be summarized. For events with varying severity, the worst reported grade will be used.

Laboratory abnormalities will be defined based on laboratory normal ranges (universal normal ranges if central laboratory) and will be summarized by visit. Selected laboratory parameters may be analyzed with shift tables and summaries of changes from baseline to worst post-treatment value. Figures of changes in laboratory parameters over time may be generated, as appropriate, for certain labs.

Change from baseline in vital sign assessments will be tabulated and summarized.

5.4.2 Demographics and Baseline Characteristics

Additional analyses will include summaries of subject demographics, baseline characteristics, compliance, and concurrent treatments. Concomitant medications will be coded and tabulated according to the World Health Organization Drug Dictionary (WHODRUG).

5.4.3 Study Treatment Administration and Compliance

Descriptive information will be provided regarding the number of acalabrutinib doses prescribed, the total number of doses taken, the number of days of treatment, and the number and timing of prescribed dose delay, interruptions, and reductions.

For each subject, acalabrutinib compliance will be described in terms of the proportion of study drug actually taken.

5.4.4 Analysis of Efficacy Parameters

Response Rate

ORR is defined as the proportion of subjects who achieve a CR or partial response (remission) (see [Section 4.2](#)). ORR will be calculated, and the corresponding 2-sided exact 95% CI will be derived.

Duration of Response

For subjects who achieve objective response, DOR is defined as the time from the first tumor assessment showing response to the time of confirmed disease progression or death due to any cause, whichever occurs first. Subjects who are still alive and free from progression at the time of data cutoff date, are lost to follow-up, have discontinued from the study, or have initiated other non-protocol antitumor therapy (NPT) will be

censored at the last evaluable tumor assessment. A Kaplan-Meier (K-M) curve will be presented for DOR and K-M median will be calculated with 2-sided 95% CI.

Progression-Free Survival

PFS is defined as the time from first dose to documented disease progression, or death from any cause, whichever occurs first. Subjects who are still alive and free from progression at the time of data cutoff date, are lost to follow-up, have discontinued from the study, or have initiated NPT will have their PFS time censored at last evaluable assessment (or, if there is no post-baseline tumor assessment, at the time of first dose). A K-M curve will be presented, and K-M estimates as well as exact 2-sided 95% CIs will be calculated for event time quartiles, and event-free rates at the protocol-specified disease assessment times.

6-month and [CCI] Progression-Free Survival Rates

PFS-6 rate is defined as the K-M estimate of subjects alive and without documented disease progression at 6 months. In this study, 1 month is defined as 30.4375 days. The K-M method will be used to estimate the PFS-6 rate and corresponding 95% CIs.

[CCI]

Overall Survival

Overall survival (OS) is defined as the time from first dose to death from any cause. Subjects who are still alive at the time of data cutoff date, are lost to follow-up, or have discontinued from the study will have their OS time censored at the last date known to be alive on or before the data cutoff date. The analysis of OS will be conducted, where applicable, using the same analysis method described for PFS.

The SAP will describe analyses of all other exploratory endpoints.

